Abbreviated Title:	SOLID
Protocol #:	19-CC-0005
Version Date:	October 7, 2019
Protocol Title:	Short or Long Infusion Duration for Platelets: The SOLID Platelet Study
NIH Principal Investigator:	[name] Department of Transfusion Medicine Clinical Center [name]
Subjects of Study:	Number: Up to 30 Sex: Either Age Range: 18 – 100 years old

PRECIS

Platelet transfusion can be a life-saving procedure in preventing or treating serious bleeding in patients who have low and/or dysfunctional platelets. Treatment of blood cancer and other blood diseases, as well as bone marrow transplantation, is not possible without platelet transfusion support. Unfortunately, 15-25% of chronically transfused patients' platelet counts will stop responding to these transfusions, putting them at risk for serious bleeding complications. The development of HLA antibodies is responsible for 4-8% of this platelet transfusion refractoriness. The presence of HLA antibodies is a clinical complication that is generally managed by the selection of products that are negative for the antigens for which the patient has antibodies. Often, for patients with chronic and ongoing need, this selection is facilitated by targeted recruitment of donors with known HLA types (i.e., types that lack antigens cognate to the patient's known antibodies and are thus predicted to be compatible). However, for very broadly HLAalloimmunized patients, compatible products may be exceedingly scarce or completely unavailable, precluding the ability to consistently provide products the patient will likely increment from. This research protocol is designed to evaluate the efficacy of a 4-HOUR continuous infusion of single donor, apheresis platelets in overcoming both alloimmune-mediated and non-alloimmune-mediated platelet refractoriness. We hypothesize that when we transfuse patients over a long duration, who have platelet refractoriness, the platelet counts will increase to higher numbers for an extended period of time in the peri-transfusion period when compared to shorter transfusion intervals.

Table of Contents

1. 1.1 1.2	OBJECTIVE. Primary Objective:	5
2.	INTRODUCTION, BACKGROUND, AND SCIENTIFIC JUSTIFICATION	6
3. 3.1 3.2 3.3	STUDY DESIGN))
4. 4.1 4.2	ELIGIBILITY ASSESSMENT 10 Inclusion Criteria 10 Exclusion Criteria 11)
5.	RESPONSE CRITERIA	1

1. OBJECTIVE

1.1. Primary Objective:

To evaluate efficacy of continuous platelet transfusions in overcoming platelet transfusion refractoriness, including HLA-alloimmune-mediated refractoriness, in patients with severe thrombocytopenia.

1.2. Secondary Objective:

To characterize the efficacy of continuous platelet infusion on bleeding outcomes, as measured during the peri-transfusion period by daily hemostatic assessments using the World Health Organization (WHO) bleeding scale (see section 6.3.4).

2. INTRODUCTION, BACKGROUND, AND SCIENTIFIC JUSTIFICATION

Rationale:

Platelet transfusion can be a life-saving procedure in preventing or treating serious complications from hemorrhage in patients who have disorders manifesting as thrombocytopenia and/or platelet dysfunction. Allogeneic platelet support is indispensable to the treatment of hematological and non-hematological diseases. Prophylactic platelet transfusion to prevent bleeding -- rather than waiting to treat active bleeding -- is now the standard practice for the treatment of profound thrombocytopenia (with platelet counts below 10 x 10⁹ cells/L) and is recommended by various clinical practice guidelines ¹⁻⁶. Higher "triggers" are recommended when invasive procedures are anticipated. In 2011, an estimated 2.1 million platelet products were transfused in the USA ⁷. However, depending on the patient, and disease characteristics, 15-25% of patients chronically transfused with leukocyte-reduced blood components will ultimately develop platelet refractoriness, making this a major worldwide health problem ⁸⁻¹⁰.

Platelet refractoriness is defined by an inadequate post-transfusion platelet count increment and is calculated based on pre- and post-transfusion platelet counts, the number of transfused platelets, and the patient's body surface area. The most commonly used definition to establish platelet refractoriness is a post-transfusion corrected count increment (CCI) less than 7500/uL 10-60 min following the transfusion (CCI_{1hr}), and less than 5000/uL at the 18-24 hrs time points ¹¹, where CCI is calculated as follows: CCI = (absolute count increment per μ L x body surface area in m²)/number of platelet transfused (x 10¹¹). The CCI is also commonly reported as a "unit-less" multiple of 1000 (i.e., a failed CCI_{1hr} would be <7.5).

Platelet refractoriness is associated with bleeding complications, reduced overall survival and longer hospital stays and higher hospital costs ¹²⁻¹⁴. The National Institutes of Health Clinical Center is a major research referral center for hematologic disorders, including severe aplastic anemia (AA), paroxysmal nocturnal hemoglobinuria (PNH), congenital thrombocytopenia, and a multitude of premalignant and malignant hematological disorders. Patients with these disorders are characterized by pancytopenia, a hypocellular bone marrow, and suppression of hematopoiesis, resulting in hypoproliferative thrombocytopenia. Further, one treatment modality that many of the Clinical Center's research protocols utilize in the treatment of hematologic and immunologic conditions is hematopoietic progenitor cell transplantation (HPCT), which relies on the recovery of the hematopoiesis from engrafting donor progenitor cells. However, until patients recover hematopoiesis they remain pancytopenic. Thrombocytopenia leads to easy bruisability and purpura, petechiae of the skin and mucous membranes, epistaxis, irregular and heavy menses, and gum bleeding. Bleeding can be brisk in the presence of accompanying physical lesions, as in gastritis and fungal infection of the lungs. The most feared complication of thrombocytopenia is intracranial hemorrhage, which has a high degree of mortality. The

The SOLID Platelet Study 10/07/19

Protocol Number: 19-CC-0005 PI: [name]. primary modality to prevent life-threatening hemorrhage is platelet transfusion ⁵. However, patients who develop platelet refractoriness do not increment appropriately to platelet transfusions. Any intervention that augments hemostasis in these patients pending the recovery of hematopoiesis and endogenous platelet count would potentially be lifesaving.

HPCT is not possible without adequate platelet support. While most platelet refractoriness is associated with a range of multifactorial non-immune-mediated clinical factors such as fever, sepsis, splenomegaly and certain medications, a significant subset of refractoriness is due to antibodies directed against foreign HLA antigens that developed as a result of exposure to foreign leukocytes through pregnancy or prior transfusion ^{8,15,16}. Management of platelet refractoriness at the Clinical Center focuses on providing platelets of HLA types compatible with the recipient's antibody profile (i.e., platelets that do not contain the HLA antigens to which the patient has developed antibodies). Providing HLA matched platelets is primarily accomplished via targeted donor recruitment or less frequently purchasing products procured from blood collection agency searches at both the regional and national level. However, for very broadly HLA-alloimmunized patients, compatible products may be exceedingly scarce or completely unavailable, precluding the platelet transfusion support necessary to overcome the patient's refractoriness.

While clinical studies have described the phenomenon of platelet alloimmunization in detail, a full elucidation of its pathophysiology remains elusive ¹⁶. The majority of clinically relevant HLA antibodies have been shown to be immunoglobulins G and M (IgG and IgM) that are directed against HLA class I epitopes, namely, HLA-A and B antigens. When patients generate IgG and IgM to allogeneic platelets, the destruction of platelets occurs by one of the known antibody dependent mechanisms, namely eradication via the Fc receptor-expressing phagocytes ¹⁷ residing in the reticuloendothelial system (RES) and via complement activation ¹⁸. However, attempts to reduce the production of HLA antibodies using immunosuppressive or immunomodulatory agents (e. g. IVIG, cyclosporine, corticosteroids) typically do not achieve a sustained resolution of platelet refractoriness ¹⁹⁻²². Our experience with a pilot trial treating HLA alloimmunemediated platelet refractoriness with eculizumab, a monoclonal antibody that inhibits complementmediated destruction by binding C5, shows that while preliminarily results indicate some promise in a subset of patients, refractoriness persists in others ²³. Thus, alternative approaches to manage patients who are heavily HLA alloimmunized are in great demand. It is also clear that alloimmunization to HLA antigens does not explain all platelet refractoriness and even for immune refractoriness, HLA alloimmunization may be a marker for other conditions (platelet-specific antibodies (HPA), non-HLA antibodies to antigens on the platelet surface).

Recently, slow, continuous infusion of platelet products (continuous platelet transfusion, CPT) has garnered renewed interest as one potential way to manage platelet transfusion refractoriness (PTR) ²⁴⁻²⁶. In a case series of three patients with PTR, Narvios *et al* reported successful post-transfusion increments after administration of platelet concentrates infused over six hours, with one patient, who also had hematuria prior to the infusion, experiencing clinical hemostasis 24-hours post-infusion ²⁴. However, details regarding the nature of the refractoriness (alloimmune vs non-alloimmune) and the CCI were not reported. In a larger, retrospective analysis of 21 patients with PTR, Tzadok *et al* evaluated the impact of 24-hour CPT -- consisting of consecutive transfusions of single-donor apheresis platelets (SDP) half-doses (i.e., comprising 1.5×10^{11} platelets each) infused over 4-6 hours each -- on the CCI obtained after 12 and 24-hours post-transfusion. The authors found CPT resulted in a statistically significant higher mean CCI at 24 hours (1.16 vs. 0.37, p<0.05) but not at 12 hours (2.45 vs. 0.36, p=0.058) ²⁵. The HLA/HPA alloimmune status of the patients was not reported. Most recently, employing a similar 24-hour CPT method as Tzadok *et al*, Cid *et al* reported a range of measures (including HLA alloimmune status, bleeding outcomes and median platelet counts before and after CPT) in their retrospective analysis of CPT in 14 patients (6 alloimmune-mediated,

The SOLID Platelet Study 10/07/19

Protocol Number: 19-CC-0005 PI: [name]. 8 non-alloimmune-mediated). The difference in increments prior to, and after, CPT was not formally statistically assessed. However, nine bleeding episodes (WHO grade>2) were present prior to 19 CPT infusions and all nine resolved during the 24-hour infusions, notably without any complicating adverse transfusion reactions ²⁶. Similar other anecdotal successes with using 24-hour CPT or massive platelet transfusion to manage bleeding risk and/or alloimmunization have also been reported ⁹.

The theoretical underpinnings of how CPT might be effective in augmenting hemostasis and minimizing bleeding events, despite PTR -- including alloimmune-mediated PTR, were the subject of recent speculation ²⁶. Briefly, it has been observed that transfusion of HLA-incompatible platelets, while not appreciably improving hemostasis as measured by 10- and 60-minute post-transfusion forearm bleeding times, nevertheless results in increases in deposition of fibrin on the subendothelial surface and in circulating thrombin-antithrombin complexes, suggesting a procoagulant effect ²⁷. The volar bleeding times were performed with positive capillary pressure. Thus, it is not known to what extent, if any, this apparent procoagulant effect may mitigate the overall bleeding diathesis that results from severe thrombocytopenia, and, in particular, in tissues with physiologic or low shear rates. Importantly, Tzadok *et al* suggests a proportion of incompatible platelets infused within a 24-hour CPT may escape immune-mediated clearance mechanisms ²⁵. An alternative hypothesis that derives some support from animal studies is that massive platelet transfusion may be able to directly reduce the level of alloimmunization by *in vivo* alloadsorption ⁹, thus increasing the likelihood of adequate CCI on each sequential platelet transfusion from donors sharing a given HLA type.

In general, a fixed 7.1×10⁹ platelets/L/day is necessary to maintain the vascular endothelial integrity ²⁸, suggesting that the average 70 kg adult with a total blood volume of ~5L would require ~0.36×10¹¹ platelets/day. A 24-hour CPT, consisting of five to six half-dose SDPs (1.5×10¹¹ platelets each) in 24 hours, would provide, at minimum, 7.5×10¹¹ platelets/L/day. In PTR, and in particular in alloimmune-mediated PTR, the minimum number of transfused platelets needed per unit time to maintain vascular endothelial integrity, mitigate bleeding risk, manage hemorrhage or obtain adequate CCIs is unknown. The kinetics of platelet survival in patients with PTR, and the increment in circulating platelet count during transfusion, is similarly unknown.

Taken altogether, these data support slow, continuous transfusion as a potential transfusion approach that may minimize the number and/or duration of adverse hemorrhagic events and that may result in greater platelet increments per unit time than the conventional infusion approach. Furthermore, there is no evidence in the published literature or any reported relevant experience of physicians who treat thrombocytopenic patients to suggest that CPT would be deleterious. Therefore there is equipoise in this trial design.

This study only utilizes Cerus Intercept Blood System (IBS) single, apheresis donor platelets (SDP) to compare two treatment approaches: 4-HOUR continuous infusion ("Long Transfusion") versus <60-minute infusion ("Short Transfusion"). The IBS is an FDA-approved pathogen reduction technology that reduces the risk of transfusion-transmitted infections by inactivating a broad range of pathogens such as viruses, bacteria and parasites that may be present in donated blood. This technology is the standard of care processing for all platelet products collected by the Department of Transfusion Medicine (DTM), implemented January 14th, 2016. The 4-HOUR infusion duration was selected as the maximum infusion time since it is undesirable for components that contain red cells to remain at room temperature longer than 4 hours, and since it is generally recommended for components to complete transfusion within 4 hours by the FDA-recognized AABB *Circular of Information*

(https://www.fda.gov/downloads/BiologicsBloodVaccines/GuidanceComplianceRegulatoryInformation/G

uidances/Blood/UCM364587.pdf, accessed 11/07/2017). Sixty-minutes was selected for the maximum duration for the "Short Transfusion" based on retrospective data on platelet transfusion durations and to proscriptively not exceed the 300 mL/hour ("or as tolerated") rate recommended by the AABB Technical Manual (18th edition). As each transfusion will use a half-SDP, and since each full SDP is no greater than 390 mL, the maximum volume in each product issued within this protocol will not exceed 195 mL; thus, ensuring that the slowest infusion rate allowed within this protocol for the "Short Transfusion" does not exceed 195 mL/hour (that is, is not prescriptively forced to exceed the 300 mL/hour recommended standard rate).

3. STUDY DESIGN

3.1. Indication:

Platelet transfusion refractoriness (PTR)

3.2. Subject Population:

Subjects/Patients with thrombocytopenia (due to congenital causes, bone marrow failure, hematologic malignancies, and treatment-related), already enrolled on a primary protocol at the NIH CC, who require platelet transfusions, as well as demonstrate PTR diagnosed by the following:

Lack of an adequate post-transfusion platelet count increment, defined by CCI <5000/ul at 10-60 minutes after each of at least 2 consecutive platelet transfusions.

If, in addition to meeting the above criteria for PTR, anti-HLA class 1 type A and/or type B antibodies are detected, the PTR will be classified as HLA-alloimmune-mediated. If HPA antibodies are detected in the setting of PTR, the PTR will be classified as HPA alloimmune-mediated.

If neither HLA nor HPA antibodies are detected, the PTR will be classified as non -alloimmunemediated. Both alloimmune and non-alloimmunte types of PTR are eligible for this study.

3.3. Randomized Block Schema:

SCHEDULED INTERVALS, DURING EACH 12-HOUR BLOCK.

4. ELIGIBILITY ASSESSMENT

GROUP A:

4.1. Inclusion Criteria

- Ability to comprehend the investigational nature of the study and provide informed consent
- Thrombocytopenia
 - a) Causes of thrombocytopenia may be due to:

- 4. Treatment related
- b) Thrombocytopenia is generally defined as one of the following:
 - 1. <10K/uL without bleeding
 - 2. <20K/uL for "complicated prophylaxis" in patient's determined to be at increased risk of bleeding or other complications
 - 3. <50K/uL with evidence of active bleeding, such as intracranial hemorrhage, GI bleeding, pulmonary hemorrhage, uncontrolled epistaxis, hematuria.

The treating provider may change the platelet transfusion threshold based on the clinical circumstance, patient population, and/or concurrent primary protocol considerations – similar to the PLADO study²⁹.

- Diagnosed with PTR, characterized by the following:
 - a) Lack of adequate post-transfusion platelet count increment, defined by, CCI <5000/ul at 10-60 min after each of at least 2 consecutive platelet transfusions
 - b) Presence of anti-HLA class 1 type A and/or type B antibody, in the setting of PTR, as defined above, constitutes the HLA alloimmune-mediated subtype of PTR. Presence of one or more HPA antibodies in the setting of PTR, as defined above, constitutes the HPA alloimmune-mediated subtype of PTR. Failure to detect HLA or HPA antibodies will be categorized as "non-alloimmune-mediated PTR."

4.2. Exclusion Criteria

- Less than 18-years-old
- Lack of ability to obtain informed consent

- Pregnant female
- Presence of ITP/autoimmune thrombocytopenia
- Immune platelet refractoriness responsive to treatment with IVIg or eculizumab, or other immunosuppressive therapy within the 3 preceding months. This is based on the wide variation in the duration therapeutic antibodies, with the upper limit frequently cited as 3 months.

5. RESPONSE CRITERIA

Statistically significant difference in the adjusted platelet increment area under the curve (AUC) obtained between 0-HOURS and 6-HOURS after the start of the platelet transfusion (Long Transfusion or Short Transfusion); this is determined at the interim and final analysis. The interim analysis will include a test of the null hypothesis of no difference in efficacy, using a threshold of significance of 0.01, with a threshold of 0.04 used for the final analysis. See *Study Analysis*, Section 8.2 for further details.

6. TREATMENT PLAN

6.1. Pre-Study Evaluation (screening)

- Conducted as part of the subject's primary research protocol:
 - Clinical history and body surface area (BSA)
 - CBC or CBC with differential
- Conducted as part of this protocol's screening:
 - PT/INR and aPTT
 - HLA typing and HLA class I A, B, C antibody screen for HLA alloantibodies
 - HPA antibody screen ("Platelet antibody screen")

6.2. Randomized Block Design

6.2.1. Randomization

- Upon IRB approval, the randomization schema for the first block for each subject will be specified using the "sealed envelope" web application at https://www.sealedenvelope.com/simple-randomiser/v1/lists, using the following input specifications:
 - 1) Treatment Groups
 - Group A: Long Transfusion followed by Short Transfusion in the first block
 - Group B: Short Transfusion followed by Long Transfusion in the first block
 - 2) Block sizes 4, 6, or 8
 - 3) List Length 30

This web application has been used for randomization in various published clinical trial studies over the last decade

(https://scholar.google.com/scholar?q="Sealed+Envelope+Ltd.").

• The randomization list will be held by the TSL Operations Coordinator, who will reveal the first block assignment (Group A versus Group B) for each subject at the time of that subject's enrollment

• Only one block per day will be permitted for a subject. Up to two further subsequent blocks (one per day) may be administered for a subject, thus bringing the total maximum number of blocks per subject to three. Subsequent blocks will alternate the sequence of the Long and Short Transfusions.

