7.1. Sample Size and Study Design

We will determine the sample size using the Two-Stage Design. At the first stage, 12 subjects will be accrued. An interim analysis will be performed to compare the platelet count AUC values, adjusted for the absolute number of platelets transfused (adjusted platelet AUC), between the within-block treatment pairs. If the difference is significant at the 0.01 one-sided level favoring

the slow infusion technique, then accrual will cease and the null hypothesis rejected. At the interim analysis we will also perform a futility analysis. If the conditional power for rejecting the null hypothesis at the end of the study is less than 0.3, then accrual will cease. Otherwise, an additional 12 subjects will be accrued, bringing the total number of subjects to n=24. To account for dropouts, up to 30 subjects will be enrolled. Anticipated dropouts are due to inability to tolerate blood draws.

This design (n=24) has power >80% using the sign test on the matched pairs from the first block for each patient under the alternative hypothesis that the probability that a matched pair of adjusted platelet AUC values favors the test regimen is 0.80, assuming no tied observations ³². The actual analysis will use the Wilcoxon matched pair signed rank test. A mixed model analysis for multiple blocks per patient will be performed as a secondary analysis.

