8.2. Study Analysis

All subjects who receive one 12-HOUR block of Short and Long infusion duration of platelets will be included in the primary analysis. Every effort will be made to evaluate the subjects before transfusion as well as at 2-HOURS, 4-HOURS and 6-HOURS after starting each platelet dose infusion. Adverse events will be tabulated by severity and attribution to treatment and disease (transfusion reactions will be classified using the CDC NHSN *Hemovigilance Module Surveillance Protocol*, which may be accessed at https://www.cdc.gov/nhsn/pdfs/biovigilance/bv-hv-protocol-current.pdf).

Final statistical analysis will be performed once all 24 subjects have completed the end of study assessments and all data have been archived for analysis. An interim analysis will be conducted after 12 subjects have completed at least one 12-HOUR block of transfusions. The planned

Protocol Number: 19-CC-0005 PI: [name]. analyses will include descriptive statistics on the proportions of platelet response and 2-HOUR to 6-HOUR platelet increment AUC values, adjusted for number of platelets given. Hypothesis testing will utilize Wilcoxon matched pair signed rank test for the primary analysis. Mixed model analysis will be employed for multiple blocks per patient and reported descriptively.

The interim analysis will include a test of the null hypothesis of no difference in efficacy using a threshold of significance of 0.01, with a one-sided threshold of 0.04 used for the final analysis. The interim analysis will also include a futility analysis based on the conditional power for rejecting the null hypothesis at the final analysis given the interim results. The futility analysis reduces the type I error of the design.

Secondary analysis based on mixed effect regression, and logistic regression analysis will also be employed if deemed appropriate.

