APPENDIX B: Protocol Worksheet

The SOLID Platelet Study, Protocol #19-CC-0005

LONG Transfusion followed by SHORT Transfusion

INSTRUCTIONS:

- All CBCs should be collected in a 2 mL EDTA tube; please WASTE the first 1 mL at each sample collection
- CBC collection times may occur (+/-) 15 minutes of the target draw time
- Documenting 'EXPECTED TIME' is optional; it is provided as a reference tool for planning the CBC collection and transfusion START / STOP Schedule
- Please call [name] (DTM, Protocol PI) with any questions, concerns, or if you run in to any problems, at [contact].

		EXPECTED TIME	ACTUAL TIME	PLATELETS	HEMOGLOBIN	
		(Optional)		(10 ⁹ /L)	(g/DL)	
1.	PRE (0-HOUR)					
	i. START Long Transfusion AFTER CBC collect	tion				
	ii. Continue transfusing over 4-HOURS					
	iii. Gently Swirl Bag for 20 revolutions every	30-min				-
	A. CBC COLLECTION					
	B. LONG TRANSFUSION START					
2.	2-HOUR (1b) + 2-HOURS					
	A. CBC COLLECTION					-
3.	4-HOUR (1b) + 4-HOURS - STOP Long Transfusion B	EFORE CBC Collection				TOE
	A. LONG TRANSFUSION STOP					BEO
	B. CBC COLLECTION					COMPLETED
4.	6-HOUR (1b) + 6-HOURS				≤P	
	i. START Short Transfusion AFTER CBC Collection					Ē
	ii. Also serves as the PRE (0-HOUR) CBC for	the Short Transfusion Tr	ansfuse for no more			Ē
	than 60-minutes					
	iii. Gently Swirl Bag for 20 revolutions every	30-minutes				
	A. CBC COLLECTION					BY DTM
	B. SHORT TRANSFUSION START					>
5.	7-HOUR (4b) + 1-HOUR - STOP Short Transfusion					
	A. SHORT TRANSFUSION STOP					
6.	8-HOUR (4b) + 2-HOURS					-
	A. CBC COLLECTION					-
7.	10-HOUR (4b) + 4-HOURS	1			-	-
	A. CBC COLLECTION					-
8.	12-HOUR (4b) + 6-HOURS					
	A. CBC COLLECTION					
		1				

Print Name of RN(s) Completing form	Signature	Date
1)		
2)		

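### Block 1's dose order is revealed at enrolment, not when the block is committed; a later reveal is a nearly free safeguard, although chance loss alone would do little harm

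*Combined protocol and SAP*

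**What the plan says.** Section 6.2.1 generates the first-block order from a web application, with "Block sizes 4, 6, or 8" and "List Length 30". The TSL Operations Coordinator holds the list and is the person "who will reveal the first block assignment (Group A versus Group B) for each subject at the time of that subject's enrollment". Later blocks are optional ("Up to two further subsequent blocks (one per day) may be administered for a subject") and their order is fixed: "Subsequent blocks will alternate the sequence of the Long and Short Transfusions".

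The primary comparison is Long against Short within block 1 (8.1), by the Wilcoxon signed-rank test with no sequence or period term (7.1, 8.2). On who is analysed, 8.2 says: "All subjects who receive one 12-HOUR block of Short and Long infusion duration of platelets will be included in the primary analysis". On numbers, 7.1 says: "To account for dropouts, up to 30 subjects will be enrolled". It expects dropouts because some subjects will not tolerate the blood draws. Section 8.4 replaces withdrawn subjects until 24 is reached and does not mention order.

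No masking is described. The Appendix B worksheet is headed "LONG Transfusion followed by SHORT Transfusion", and Appendix C names the reverse order. Under 6.3.1, the 6-hour count that closes dose 1 is also the 0-hour count of dose 2.

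**The concern.** Every completed block contains both infusion durations, so the order of the two doses is the only thing this trial randomises. The signed-rank test makes no allowance for order. If the first and second doses differ for reasons unrelated to duration, only equal numbers of Long-first and Short-first pairs cancel that difference. The shared 6-hour count makes such a difference plausible: platelets from dose 1 that are still clearing pull dose 2's net AUC down.

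Revealing the order at enrolment opens a gap before the block. A subject who leaves in that gap has used a list slot and contributes no pair, which can undo the permuted-block balance. Within the gap, the decision to start, delay or abandon the block can also be taken with the order known.

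**Working it through.** **1. The plan's own figure.** Section 7.1 claims power above 80% for a sign test on 24 pairs with a 0.80 chance that a pair favours Long. At one-sided 0.04 the critical count is 17 of 24. The exact error is P(X ≥ 17 | 24, 0.5) = 0.032, and the power is P(X ≥ 17 | 24, 0.8) = 0.911. The claim reproduces. It takes no account of dose order.

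**2. Is there a gap?** Enrolment is not tied to a transfusion day. Before a block, a suitable in-house component must be available and split (6.2.2). The treating provider may move the transfusion threshold (4.1). A subject may withdraw or stop needing platelets (8.4). A gap is therefore possible, but its length is not stated.

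**3. Balance under chance loss.** Permuted-block lists (sizes 4, 6 and 8 at random, 1:1 assumed) of 24 + m slots were simulated, with m slots removed at random (20,000 lists). The plan allows 30 − 24 = 6 spare places.

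| Lost between reveal and block (m) | 14:10 or worse, either direction | Long-first 15:9 or worse |
|---|---|---|
| 0 | 0.3% | 0 |
| 2 | 6% | 0.04% |
| 4 | 14% | 0.5% |
| 6 | 20% | 1.4% |

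With m = 0, only the last, incomplete block can be unbalanced. A block of 8 gives an excess of at most 4, so 14:10 is the worst possible split.

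**4. What an imbalance does.** Assumptions, none of them from the documents: one compartment, unit doses, identical recovery and clearance for both doses, Long over 4 h, Short over 1 h, dose 2 starting at hour 6, normal noise with pair SD 50% of the Short AUC. The AUC is the plan's trapezoid at 0, 2, 4 and 6 h above each dose's own 0-hour count. Long minus Short, as a fraction of the Short AUC:

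| Half-life | Long-first pairs | Short-first pairs | Gap | Rejection at 12:12 | Rejection at 15:9 Long-first |
|---|---|---|---|---|---|
| 3 h | +0.40 | −0.32 | 0.72 | 3.6% | 17% |
| 4 h | +0.30 | −0.36 | 0.66 | 1.0% | 5.9% |
| 6 h | +0.18 | −0.36 | 0.54 | 0.2% | 1.5% |
| 12 h | +0.02 | −0.32 | 0.34 | ≤0.2% | ≤0.2% |
| 24 h | −0.08 | −0.27 | 0.19 | ≤0.2% | ≤0.2% |

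Rejection is one-sided at nominal 0.04 with n = 24 (10,000 runs per split). Going from 12:12 to 15:9 moves the mean by (3/24) × gap: 0.125 × 0.72 = 0.09 of the Short AUC at 3 h, and 0.125 × 0.66 = 0.08 at 4 h.

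**5. Average over the splits that occur.** Average error = Σ P(split) × rejection rate at that split. From m = 0 to m = 6 it moves from about 3.75% to 4.4% at 3 h, from 0.9% to between 1.1% and 1.2% at 4 h, and from 0.2% to 0.3% at 6 h. Splits that favour Short-first lower the rejection rate and offset much of the rise.

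**6. Loss that depends on order.** If 10% of one order and 30% of the other were lost (an assumption; lists were allowed to run past 30 to reach 24 pairs), 14:10 or worse would occur in 50% of lists and 15:9 or worse in 20%. At 5% against 35% the figures are 73% and 41%. Such loss pushes the split in one direction, so the offset in step 5 no longer protects. The documents give no basis for choosing among these rates.

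**The case against.** The strongest case against is that the early reveal has almost no measurable consequence, and much of this stands.

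- **Chance loss.** A reader might pair the 20% chance of imbalance with the 17% rejection rate and infer serious error inflation. The two do not belong together. The 20% is for 14:10 or worse in either direction; the 17% is for 15:9 in the harmful direction at the fastest clearance tried. That split or worse occurs in at most 1.4% of lists. The background (section 2) calls platelet kinetics in refractory patients unknown.
- **Where dropout falls.** Section 7.1 expects losses from intolerance of blood draws. Those would mostly occur during the block, after any reveal, so six losses in the gap is an upper limit.
- **Outstanding antibody tests.** HLA and HPA testing may be done on enrolment (6.3.2), but it only classifies the refractoriness and both types are eligible (3.2). It is weak evidence of a delay.
- **Selection.** The order is hidden until enrolment, so who is enrolled cannot depend on it. No passage suggests that staff would favour one order. A paired test must leave out subjects who have no pair.
- **Blocks 2 and 3.** A reader might infer that the predictable alternation threatens the result. The primary analysis uses block 1 only, and later blocks feed a mixed model reported descriptively. Alternation also balances order within a subject who has two blocks. Replacing it is a trade-off, not a correction.
- **Analysis instead.** A sequence-adjusted test holds error at 0.039 to 0.041 for splits from 12:12 to 16:8 at almost no cost in power. That handles unequal numbers. It does not prevent starting or delaying blocks according to order.

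What remains is that the plan leaves the gap open without need, and closing it costs almost nothing.

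**Conclusion.** The point holds as a free improvement, not as a threat to the primary result. The order is known from enrolment, an unused assignment still consumes a list slot, and nothing restores balance by order. Under chance loss alone the harm is small: even with all six spare places in the gap, the average one-sided error rises by about 0.65 percentage points (4.4 − 3.75) at a 3 h half-life, and stays near 1% or less at 4 h or longer. These figures rest on the assumed one-compartment model, equal kinetics, a pair SD of 50% of the Short AUC and random loss. The real value of a later reveal is protection against order-dependent starting or loss, which the documents neither show nor exclude and whose size cannot be derived from them. That the trial is open is an inference from the lack of any masking and from the worksheets.

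**What to change.** In 6.2.1, change the timing in the sentence on the reveal so that the coordinator discloses the first-block assignment when the split component for the subject's first block is issued, after screening is complete and the decision to start the block is recorded. State that a list slot is used only at that moment. Leave the alternation in blocks 2 and 3 as it is.

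The cost is a one-paragraph amendment. No patients, procedures or staff are added: the list holder is TSL staff, and the component is split under TSL procedures. Nurses would receive the Appendix B or C worksheet at issue instead of earlier. The change does not address losses during the block, such as missed counts or intolerance of blood draws.
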